3.0 Experimental Design and Methods

We hypothesize that treatment with hydroxychloroquine may offer a safer and effective method to control disease activity in HS. We hypothesize that the profiling inflammatory cytokines in the peripheral blood of the patients with HS may provide novel therapeutic targets for the disease. Additionally, monitoring of inflammatory cytokines before and after treatment may help to explain the mechanism by which therapies work. Over the proposed period, we intend to gather data about patient response to treatment with hydroxychloroquine and about the cytokine profile of patients with HS. Sequential patients will be assigned to hydroxychloroquine treatment. Patients will be evaluated at baseline and after 3 months of treatment for treatment response and to evaluate quality of life measures. Serum will be collected at baseline and following 3 months of treatment. Peripheral blood from patients with HS will be analyzed for levels of cytokines thought to be involved in HS and several markers of inflammation that have not yet been analyzed in this disease.

Treatment

Patients will have baseline CBC and CMP evaluation prior to initiation of therapy
Sequential patients will be assigned treatment with hydroxychloroquine 200mg BID
Treatment length will be 3 months

Evaluation of HS

Patients will be evaluated at baseline and at 3 months by:

Hurley staging:

Stage 1: solitary or multiple, isolated abscess formation without scarring or sinus tracts

Stage 2: recurrent abscesses, single or multiple widely separated lesions, with sinus tract formation

Stage 3: diffuse or broad involvement, with multiple interconnected sinus tracts and abscesses

Number of inflammatory nodules, abscesses, fistulas, scars, locations of these lesions, longest distance between 2 relevant lesions, are lesions separated by normal skin (for Sartorius scoring)

Improvement in HS lesions

Sartorius score: A statistically significant decline in Sartorius scoring between baseline and end of treatment

Evaluation of quality of life

Patients will be asked to fill out Dermatology Life Quality Index (DLQI) survey at baseline and 3 months. It is a simple, validated 10-question questionnaire. Answers to the questionnaire will be entered into a database.

For general inflammatory skin conditions a change in DLQI score of at least 4 points is considered clinically important

Serum for evaluation

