4.0 Human Subjects

Protection of Human Subjects

Human Subjects Involvement, Characteristics, and Design. The racial, gender and ethnic characteristics of the proposed subject population will reflect the demographics of Pittsburgh and the surrounding area and/or the patient population of the UPMC Health Systems. We shall attempt to recruit subjects in respective proportions to these demographics. No exclusion criteria will be based on race, ethnicity, gender, or socioeconomic status. The numbers of enrolled male to female subjects will be consistent with and reflective of the numbers of patients seen in the UPMCHS clinics and in approximate 1:1 proportion.

Sources of material.

Information on the subject's medical history will be obtained relative to the inclusion and exclusion criteria. Data collection methods will include data obtained specifically for research purposes based on the most recent office note. All records related to this research study will be stored in a locked file cabinet. The subject's identity on these records will be indicated by a case number rather than by name, and the information linking these case numbers will be kept separate from the research records.

Recruitment

Potential subjects with Hurley stage I/II hidradenitis suppurativa will be identified by the

examining physician and referred for evaluation by the principal investigator or co-investigator. Subjects will be recruited from the UPMC dermatology department clinics. Potential subjects will be evaluated by the Principal Investigator, who is also the treating physician, during a routine clinic visit prior to any screening procedures or evaluation of the medical record for research purposes. Potential subjects will be approached by physicians directly involved in their care. No “cold calling” will occur. Informed consent will be obtained on all subjects by the principal investigator prior to all screening procedures. If for any reason, a subject is excluded or resigns during the course of study, a new subject will be enrolled.

Inclusion Criteria

Enrolled HS patients must be Hurley stage I or II (defined above)

Patients may be on topical therapy only, and/or have completed non-immunosuppressive therapy at time of enrollment.

Subjects must be 18 years of age and must be able to understand the written informed consent.

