No evidence of active infection, regardless of the degree of severity or localization. Subjects with active infections (whether or not they require antibiotic therapy) may be eligible after complete resolution of the infection. Subjects on antibiotic therapy must be off antibiotics for at least 7 days before beginning treatment.

Exclusion criteria

Subjects currently on systemic immunosuppression are ineligible

Subjects under 18 years of age

Due to small risk of retinopathy, hepatic disease, psoriasis exacerbation, exacerbation of porphyria cutanea tarda (PCT) in patients treated with hydroxychloroquine, subjects with known retinal disease, hepatic disease, psoriasis and PCT will be excluded

Due to potential fetal risk with use of hydroxychloroquine, pregnant patients or those planning to become pregnant will be excluded

Risks to the subjects:

- i. The risks of the study are minimal and are related drug therapy and to obtaining the blood samples needed for our analysis.
 1. Physical.
 - a) Small likelihood of drug toxicity. Hydroxychloroquine has been used for many years and is known to have a mild side effect profile.
 - b) Small likelihood of infection or bleeding. Risks minimized by proper protective equipment and hygiene
 2. Psychological. There is a small likelihood of low psychological risk if participants are upset by request to be involved in the study

7. Benefits

- i. Benefits may accrue to patients with HS. Benefits may accrue to study subjects who participate through greater awareness leading to greater individual and community empowerment, enhanced knowledge of community assets as well as health concerns and needs, and enhanced skills related to performance of duties as study subjects. Outside of participants in research, all community members may also benefit from enhanced trust and reciprocity within the community.

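### Pregnancy is excluded because of fetal risk, but the protocol text available names no pregnancy test before the first dose of hydroxychloroquine

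*Combined protocol and SAP*

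**What the plan says.** Section 4.0, Exclusion criteria, sets the rule and gives the reason for it: "Due to potential fetal risk with use of hydroxychloroquine, pregnant patients or those planning to become pregnant will be excluded".

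Section 3.0, Treatment, sets out what happens before and during dosing. On laboratory work ahead of the drug, it says "Patients will have baseline CBC and CMP evaluation prior to initiation of therapy". The regimen is given as "Sequential patients will be assigned treatment with hydroxychloroquine 200mg BID", and its duration by the line "Treatment length will be 3 months". Evaluations are scheduled at baseline and at 3 months. The enrolment research sample is a single 10 ml tube, kept for banking and cytokine measurement.

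On how eligibility is checked, section 4.0, Sources of material, says that "medical history will be obtained relative to the inclusion and exclusion criteria". Under Recruitment, "Potential subjects will be evaluated by the Principal Investigator, who is also the treating physician, during a routine clinic visit". That sentence goes on to place the evaluation ahead of any screening procedures, and the same paragraph later says that consent comes before all of them. Section 8.0 also speaks of screening procedures as having been described earlier in the document. No list of them appears in the text available.

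**The concern.** The protocol itself judges that fetal risk is reason enough to keep pregnant patients off the drug. An exclusion of this kind works only if some step before dosing can find the patients it is meant to exclude. Asking about plans to conceive is a matter of history, and so is asking about a pregnancy that the patient knows of. An early pregnancy that she is unaware of is not, and finding it takes a test.

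If no test is required, a site could follow the text to the letter and still give hydroxychloroquine to a patient whom the protocol means to exclude. At stake is the safety of that patient and the fetus. The Sartorius comparison, the cytokine comparison and the sample size do not depend on this point.

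**Working it through.** The protocol states no figure to reproduce here. The check sets each pre-dose step in the text against one question: could it find a pregnancy that the patient does not know about?

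1. **CBC and CMP** (section 3.0, Treatment): no. These are a blood count and a chemistry panel.
2. **Research tube at enrolment** (section 3.0, Serum for evaluation): no. It is assigned to banking and cytokines.
3. **Medical history** (section 4.0, Sources of material): no. It can find a known pregnancy or a plan to conceive. That it cannot find an unknown one is an inference, not something the protocol states.
4. **Investigator's evaluation at a routine visit** (section 4.0, Recruitment): nothing in the text attaches a pregnancy test to it.
5. **Screening procedures** (section 4.0, Recruitment; section 8.0): cannot be judged, because their content is not given.

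The rest of the text does not fill the gap. Pregnancy as a patient condition appears only in the exclusion sentence. The related mentions elsewhere are the teratogenic effects of tetracyclines (section 2.0) and birth defects in the definitions of seriousness (section 6.0), and neither is a test. No visit is scheduled between baseline and month 3. There is no contraception requirement and no stopping rule specific to pregnancy.

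The number of tests needed to close the gap follows from two inputs: 20 patients (section 5.0) and men and women enrolled "in approximate 1:1 proportion" (section 4.0).

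- At 1:1: 20 × 1/2 = 10 women, so about 10 tests.
- If every patient were a woman: 20 × 1 = 20 tests. This bound is worth showing because section 2.0 says that the disease mainly affects women.
- The share of childbearing potential is not given, so the number of enrolled patients needing a test could lie anywhere from 0 to 20. Each replacement, or extra woman screened, adds one.

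No probability of an unrecognised pregnancy can be calculated, because the documents give neither the number of women of childbearing potential nor a rate.

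**The case against.** The strongest reply is that the protocol does provide for a screening step after the investigator's evaluation. It mentions that step more than once, and nothing says that CBC and CMP are all of it. A pregnancy test may be among the procedures that are not itemised, or may be set out in the consent document, which was not available. On that view this is a drafting gap and not a missing safeguard. Part of this stands: it limits the claim to what the available text names. It does not remove the point. The Treatment, Sources of material, Recruitment and Exclusion criteria sections are all present, a test would be expected in one of them, and none names one.

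A second reply is that treatment may be stopped when a patient's condition changes (section 3.0). That would cover a pregnancy once recognised, but someone has to recognise it first.

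A reader might also infer more than the documents support:

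- *That patients were, or would be, dosed without a test.* The text shows only that no test is named. It says nothing about what the clinic did or would do.
- *That the wording deliberately extends to unrecognised pregnancy.* The preceding criterion says "subjects with known retinal disease, hepatic disease, psoriasis and PCT will be excluded", and the pregnancy criterion lacks that first qualifier. In a short pilot protocol this may be no more than a difference in phrasing, and the point does not need it.
- *That a full 3-month course measures the risk.* The total dose says nothing about likelihood or harm, and reaching it would require the pregnancy to go unrecognised throughout.
- *That listing birth defects as serious is a judgement about this drug.* It is a standard definition. The only drug-specific statement is the potential fetal risk named in the exclusion.

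**Conclusion.** The point holds in a limited form. The available protocol excludes pregnant patients because of fetal risk, names no pregnancy test, and refers to screening procedures without saying what they are. As written, the stated procedures cannot enforce the exclusion for a pregnancy unknown to the patient.

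This rests on two things: the inference about what history can reveal, and the assumption that the pages not seen do not already require a test. If they do, what remains is a mismatch between documents, and the protocol should be brought into line.

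The size of the risk is not quantified and cannot be from these documents. This is a cheap improvement in patient safety. It is not a flaw in the analysis, and it does not undermine the trial.

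**What to change.** In section 3.0, Treatment, extend the line on baseline laboratory work with: *Women of childbearing potential will also have a negative pregnancy test (serum hCG on the same blood draw, or urine), with the result reviewed before the first dose of hydroxychloroquine.* Define childbearing potential in the same place, and list the screening procedures that sections 4.0 and 8.0 refer to. If the consent document already requires a test, make the protocol match it.

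The cost is one low-cost assay for each such woman: about 10 at a 1:1 ratio, at most 20, plus replacements and extra women screened. Serum hCG can use the blood already drawn for the CBC and CMP, so no added invasive procedure is needed. There may be a short wait before dosing or an extra screen failure. Sample size and analysis stay as they are, since section 4.0 already provides for replacing excluded subjects.

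A single baseline test does not cover conception during treatment. That would need separate measures, such as a contraception requirement and an explicit rule to stop the drug if pregnancy occurs.

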5.0 Statistical considerations

1. Sample size

- i. The study will involve 20 patients with hidradenitis suppurativa
- ii. The comparison of baseline Sartorius scores and level of the measured cytokines in peripheral blood from HS will be compared using a two-sided t test with a p value <0.05 for statistical significance.
- iii. The probability is 80% that the study will detect a difference at a two-sided 0.05 significance level if the true difference between groups is 30%.

6.0 Adverse Reaction Reporting Requirements:

This study will use the CTC version 2.0 for toxicity and Adverse Event reporting. A copy of the CTC version 2.0 can be downloaded from the CTEP home page (<http://ctep.info.nih.gov>). All appropriate treatment areas should have access to a copy of the CTC version 2.0. All Serious Adverse events that require reporting to the FDA will be reported on the FDA 3500 medwatch form found in Appendix B

- i. The following adverse reactions must be reported in the manner described below.
- ii. All adverse events which are considered to be related to the research study must be reported to the University of Pittsburgh Cancer Institute (UPCI)
- iii. All serious adverse events that meet the University of Pittsburgh Institutional Review Board's criteria for reporting can be found at (<http://irb.pitt.edu>)

	Unexpected, fatal or life threatening and associated with study drug	Unexpected, of moderate or greater severity (But not fatal or life threatening) and are associated with the research intervention	Serious, unexpected event that is associated with the study drug	Unexpected fatal or life-threatening experience which is associated with the study drug
Call to UPCI within 24 hours at [contact]	X			
Notify IRB within 24 hours	X			
Notify UPCI as soon as		X		

possible & local IRB within 10 days				
FDA notification within 15 days			X	
FDA notification within 7 days				X

An adverse reaction is considered *serious* if it is fatal or life-threatening; requires or prolongs hospitalization; produces a disability; or results in a congenital anomaly/birth defect.

An adverse reaction is considered to be of *moderate or greater severity* if it requires medical evaluation (such as additional laboratory testing) and/or medical treatment; or if it is a serious adverse reaction.

An adverse reaction is considered to be *unexpected* if it is not identified in nature, severity or frequency in the current IRB-approved research protocol or informed consent document.

An adverse reaction is considered to be *associated with the research intervention* if there is a reasonable possibility that the reaction may have been caused by the research intervention (i.e., a causal relationship between the reaction and research intervention cannot be ruled out by the investigators).

UPCI requires ADRs to be reported on the Medwatch form and on the University of Pittsburgh IRB adverse event form. The University of Pittsburgh Adverse event form must be signed by the treating investigator.

(See Appendix A for copies of the Adverse event reporting forms).

iv. FDA Guidelines for Adverse Event Reporting

All adverse events meeting the definition of serious, unexpected and associated to the research intervention will be reported to the IRB according to their guidelines found at (<http://irb.pitt.edu>):

Associated with the use of the drug. There is a reasonable possibility that the experience may have been caused by the drug.

Disability: A substantial disruption of a person's ability to conduct normal life functions.

Life threatening adverse drug experience. Any adverse drug experience that places the patient or subject, in the view of the investigator, at immediate risk of death from the reaction as it occurred, i.e., it does not include a reaction that, had it occurred in a more severe form, might have caused death.

Serious adverse drug experience: Any adverse drug experience occurring at any dose that results in any of the following outcomes: death, a life threatening adverse drug experience, inpatient hospitalization or prolongation of existing hospitalization, a persistent or significant disability/ incapacity, or a congenital anomaly/birth defect. Important medical events that may not result in death, be life threatening, or require hospitalization may be considered a serious adverse drug experience when, based upon appropriate medical judgment, they may jeopardize the patient or subject and may require medical or surgical intervention to prevent one of the outcomes listed in this definition

Unexpected adverse drug experience: Any adverse drug experience, the specificity or severity of which is not consistent with the current investigator brochure; or, if an investigator brochure is not required or available, the specificity or severity of which is not consistent with the risk information described in the general investigational plan or elsewhere in the current application, as amended. "Unexpected," as used in this definition, refers to an adverse drug experience that has not been previously observed (e.g., included in the investigator brochure) rather than from the perspective of such experience not being anticipated from the pharmacological properties of the pharmaceutical product.

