1.0 Specific Aims

To evaluate the efficacy of hydroxychloroquine as a treatment for hidradenitis suppurativa (HS)
We will conduct a pilot trial of standard dosing of hydroxychloroquine in patients with HS

To identify biomarkers as possible therapeutic targets for the treatment of HS
We will evaluate the levels of inflammatory cytokines in the peripheral blood of patients with HS.

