Hydroxychloroquine, initially developed as an antimalarial, has been used successfully for over 70 years in the treatment of autoimmune disease. Its mechanism of action is still poorly understood, but it has been shown to have many varied immunomodulatory properties ¹¹. Evidence suggests that hydroxychloroquine has an effect on inflammatory disease through decreasing levels of TNF α ¹² and Th-17 cytokines (including IL-6, IL-17 and IL-22)¹³. Additionally, studies have shown a beneficial effect of hydroxychloroquine on lipid metabolism and glucose ¹⁴. Patients with rheumatoid arthritis (which similarly to HS has an independent association with cardiovascular disease) who were treated with hydroxychloroquine had an overall decreased incidence of cardiovascular events ¹⁵. Hydroxychloroquine has a relatively benign safety profile, with retinopathy being the most concerning long term side effect. The retinopathy caused by hydroxychloroquine is reversible if identified early, and standard protocols for the use of this medication include yearly ophthalmologic examination.

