Peripheral blood will be collected at baseline and after 3 months of treatment. A 10 ml red top tube of venous blood will be obtained from patients at the time of enrollment and at month 3 for banking and cytokine analysis. The red top tubes will be centrifuged, sera will be aliquoted, logged in the database and stored indefinitely at -80°C without identifiers by a technician in [name] laboratory.

Cytokine analysis

Using an inflammatory cytokine panel, levels of cytokines including L-1 β , IL-4, IL-6, IL-10, IL-17A, IL-17F, L-21, IL-22, IL-23, IL-25, IL-31, IL-33, IFN- γ , sCD40L and TNF- α will be evaluated at baseline and 3 months. Analysis will be performed at the University of Pittsburgh Cancer Institute Luminex core facility using multianalyte profiling. Levels will be compared to age, sex and BMI matched controls in our database.

Therapy may be discontinued for any of the following reasons:

Unacceptable adverse event(s),

Patient decides to withdraw from the study, or

General or specific changes in the patient's condition render the patient unacceptable for further treatment in the judgment of the investigator.

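### Fifteen named cytokines are each called statistically significant at unadjusted p<0.05, with no multiplicity control and no exploratory label

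*Combined protocol and SAP*

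**What the plan says.** Biomarker work is one of the two aims in section 1.0: "To identify biomarkers as possible therapeutic targets for the treatment of HS". Section 3.0 (Cytokine analysis) describes the measurements: "Using an inflammatory cytokine panel, levels of cytokines including", followed by 15 named analytes, each measured at baseline and at 3 months. The introduction to section 3.0 adds "several markers of inflammation that have not yet been analyzed in this disease".

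Two comparisons are described. One is over time, since "monitoring of inflammatory cytokines before and after treatment may help to explain the mechanism by which therapies work". The other is against an external group: "Levels will be compared to age, sex and BMI matched controls in our database".

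Section 5.0, item 1.ii, sets one decision rule and applies it to the Sartorius score and the cytokines alike: the "measured cytokines in peripheral blood from HS will be compared using a two-sided t test with a p value <0.05 for statistical significance". No section gives an adjustment, a false discovery rate, a test order or a primary cytokine. None says that the cytokine p values are exploratory.

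**The concern.** Item 1.ii attaches the term statistical significance to each cytokine separately, at a level suited to a single test. Across 15 tests some nominal results are expected by chance, and the plan gives a reader no means of telling them from the rest.

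The panel is mixed. Some analytes have prior support in section 2.0. Others are there because they have not been studied in this disease. The rule describes a hit in either group in the same words. Section 7.0 plans journal manuscripts, so those words will reach people who choose the next targets to study. At stake is effort spent following up false leads.

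**Working it through.** **Inputs from the document.** 20 patients, two-sided 0.05 per test and a t test (section 5.0). The cytokines named in section 3.0 are IL-1β, IL-4, IL-6, IL-10, IL-17A, IL-17F, IL-21, IL-22, IL-23, IL-25, IL-31, IL-33, IFN-γ, sCD40L and TNF-α, which makes 15.

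**Assumptions.** The document gives no cytokine effect sizes, SDs, distributions or correlations. The calculations take one paired contrast (baseline to month 3), normal differences and, unless stated, independent tests.

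**The plan's own figure.** Section 5.0 states 80% power for a 30% difference. It gives no SD, endpoint or form of t test, so the figure cannot be reproduced. For a paired t test with n = 20 at two-sided 0.05, noncentral-t power is 80% at a standardised change of 0.66. That corresponds to an SD of differences of 30/0.660 ≈ 45% of the reference mean. The 0.66 SD is used below as the assumed size of a real change; it is not a documented cytokine effect.

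**How many cytokines might truly change.** Section 2.0 reports that hydroxychloroquine lowers TNF-α and "Th-17 cytokines (including IL-6, IL-17 and IL-22"). Counting IL-17A and IL-17F separately, that is 5 of the 15. Section 2.0 also reports raised IL-17, IL-23, TNF-α, IL-10 and IL-1β in HS, which adds IL-1β, IL-10 and IL-23 and makes 8. Most of that second evidence is from lesional skin, so it bears less directly on change in blood under treatment. Cases of 3 and 1 real changes are included to show the range.

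**Some cytokines truly change.** Simulation with 15 tests, n = 20, 0.66 SD and 40,000 runs per row. False share means the average proportion of significant calls that are false, among trials with at least one call. BH is Benjamini-Hochberg at 0.05.

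| Real changes | False share, unadjusted | False share, BH | Power per real cytokine, unadjusted | Power, BH |
|---|---|---|---|---|
| 8 | 5% | 2% | 80% | 65% |
| 5 | 10% | 4% | 80% | 56% |
| 3 | 17% | 5% | 80% | 48% |
| 1 | 37% | 11% | 80% | 39% |

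A hand check uses expected counts with m real changes: (15 − m) × 0.05 / [(15 − m) × 0.05 + m × 0.80].

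- m = 8: 0.35/6.75 = 5%
- m = 5: 0.50/4.50 = 11%
- m = 3: 0.60/3.00 = 20%
- m = 1: 0.70/1.50 = 47%

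This pools calls over all trials, so it exceeds the per-trial average, most of all when few changes are real. The pattern is the same.

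Correlation between cytokines matters little with 5 real changes: the unadjusted share stays near 10% for common correlations from 0 to 0.7. With 1 real change it falls from 37% to about 22% at 0.7.

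**No cytokine truly changes.** Expected false positives are 15 × 0.05 = 0.75. The chance of at least one is 1 − 0.95^15 = 0.537 under independence. Simulated values at common correlations of 0.3, 0.5 and 0.7 are 47%, 37% and 27%. With skewed data (lognormal, log-SD 1, independent analytes) the actual size per test is about 3.6%, and the chance of any false positive about 42%.

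**The case against.** **The wording is already tentative, and the study is a 20-patient pilot.** The aims speak of possible targets, section 3.0 says profiling may help, and no decision on treatment or efficacy hangs on a cytokine p value. This stands as a limit on weight, and strict familywise control would be out of proportion here. It does not remove the point, because item 1.ii states how these p values will be read, and it says statistical significance.

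**The 54% figure assumes that nothing changes.** Section 2.0 gives reasons to expect otherwise. This stands. A reader might infer that a cytokine finding is more likely than not to be false; the document does not support that. With 5 to 8 real changes of the assumed size, the false share is about 5% to 10%.

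**The size of the family is uncertain.** A reader might infer from the open list that analytes could be added after seeing data, or might count 30 or more tests across both comparisons. Neither is established. The analytes come from a panel run at a core facility, and item 1.ii does not say which comparison the t test covers. Both are mostly missing detail, and the calculation rests only on the 15 named cytokines and one contrast.

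**Adjustment costs power.** This stands if an adjusted threshold becomes the criterion. It does not apply to an exploratory label with full reporting.

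**Conclusion.** The point holds as a modest, inexpensive improvement. The rule in item 1.ii would label chance cytokine results statistically significant, and no other text qualifies it.

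The size depends on an unknown, the number of cytokines that truly change. Over the cases examined, Benjamini-Hochberg cuts the false share by half or more. The benefit is small if the prior evidence in section 2.0 carries over to blood under treatment, and substantial if only one or a few cytokines respond. These figures rest on an assumed 0.66 SD change, normal data, independent tests and one paired contrast. The comparison with matched controls was not modelled, because the number of controls is not given.

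A reader might also infer that the efficacy result is compromised. It is not: the Sartorius comparison is a separate test that does not depend on any cytokine result.

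**What to change.** In section 5.0, item 1.ii:

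1. Keep p<0.05 as the criterion for statistical significance for the Sartorius score only.
2. State that the cytokine tests are exploratory and that nominal p<0.05 alone will not be called statistically significant.
3. Report every cytokine assayed with effect size, 95% CI, unadjusted p value and Benjamini-Hochberg adjusted p value. Name the contrasts tested (baseline to month 3; HS versus matched controls) and treat each as its own family.
4. If the word significant is used for a cytokine at all, require adjusted p<0.05.

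The cost is a few sentences and a little extra analysis. The exploratory label with full reporting leaves the test and its power unchanged, though some nominal results become leads only. If the team uses the adjusted criterion, power for a 0.66 SD change falls from 80% to between about 39% (1 real change) and 65% (8 real changes). That is a real loss with 20 patients, and a reason to rely mainly on estimates and intervals.
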